### 11.4 Efficacy Analyses

Efficacy summaries will be provided for the Intent to Treat and Per Protocol populations.

Descriptive statistics (N, arithmetic means, SD, minimum, median, maximum) for all continuous values and frequency tables for categorical variables will be created. With regard to primary and secondary objectives as descriptive statistical evaluation, absolute and relative frequencies of number of observations will be presented together with 95 %- confidence intervals.

In case of missing values the last-observation-carried forward principle shall be applied.

A statistical testing procedure Chi-Quadrat test or alternatively a binomial testing procedure will be applied. In case of small sample sizes alternatively Fisher's exact test may be applied. Other tests may be applied as required and these will be enumerated in the Statistical Analysis Plan (SAP).

Further details of the statistical evaluation procedure will be presented in the Statistical Analysis Plan (SAP). Analysis sets (ITT population, safety population, per-protocol population, rational for exclusion from any population) will also be specified in the SAP.

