2.1. General Statistical Methods

Efficacy summaries will be provided for the Intention to Treat and Per Protocol Populations. Safety summaries will be provided for the Safety Population.

Descriptive statistics (N, arithmetic means, SD, minimum, median, maximum) for all continuous values and frequency tables for categorical variables will be created. With regard to primary and secondary objectives as descriptive statistical evaluation, absolute and relative frequencies of number of observations will be presented together with 95% confidence intervals on the proportion of success and the difference compared to Vehicle Cream.

If the method to handle missing observations is not explicitly defined (i.e. Percent Change from Baseline in Actinic Keratosis Lesion Count), two principles will be applied to adjust for missing observations: last observation carried forward (LOCF) and multiple imputations (MI). Last observation carried forward will be derived in the analysis datasets while the multiple imputations method will be performed using SAS procedures PROC MI and PROC MIANALYZE.

If there are at least 5 observations in each cell in the 2 x 2 table (when comparing treatment groups to Vehicle), the Pearson's Chi Square test will be used. If there are not at least 5 observations in each cell in the 2 x 2 table (when comparing treatment groups to Vehicle), the Fisher's exact test will be used.

A Documentation of Statistical Decisions will be created, reviewed and signed (with appropriate signatures) prior to database lock. This document will document:

- On a subject level, which populations the subject is included in and reason for exclusion if a subject is excluded from a population.
- The details of any decision made (i.e. how data is handled in the analysis or the addition of any outputs) based on the actual data collected.
- Any known issues with the data quality and how that data is handled in the analysis, and
- Any other unexpected findings that require documentation prior to database lock.

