2.6. Efficacy

Primary endpoint

For statistical assessment of the primary endpoint with a significance level of 0.05 the following underlying hypotheses are used:

$H_0: p_1 \leq p_2$ vs. $H_a: p_1 > p_2$

Where p_1 is the treatment effect of 2.5% DFD-07 (celecoxib) Cream twice daily and p_2 is the treatment effect of the Vehicle Cream preparation.

Secondary endpoints

For statistical assessment of all product comparisons after certain period of treatment (i.e. at Visits 3, 4, 5 and 6) with a significance level of 0.05, the following underlying hypotheses are used:

$H_0: p_1 \leq p_2$ vs. $H_a: p_1 > p_2$

Where p_1 is the treatment effect of 1.25% or 2.5% DFD-07 (celecoxib) Cream once daily and p_2 is the treatment effect of the Vehicle Cream preparation.

For the percent change from baseline in AK lesion counts, the Mann-Whitney U-test (Wilcoxon rank sum test) will be used to test for treatment differences compared to the Vehicle Cream preparation at a significance level of 0.05.

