2.8. Sample Size and Power Considerations

The sample size estimation of this trial is based on the assumption that the Active product exhibits a complete clearance of the AK lesions in 45% of the subjects, while the Vehicle does so in 20% of the subjects (a difference of 25% between active and Vehicle treatment groups). Assuming a power of 80% and α of 0.05, in order to demonstrate the statistical significance of such an effect difference, 54 patients per treatment group would be needed.

Considering the exploratory dose-response character of the trial, and assuming a drop-out rate of 10%, 60 subjects need to be recruited in each treatment group. With 4 treatment groups in the study, it is planned to recruit approximately 240 subjects in the study.

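### SAP 2.1 chooses Pearson or Fisher by observed instead of expected cell counts; this costs power where Vehicle clearances are few but does not affect the primary test at the planned rates

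*SAP*

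**What the plan says.** SAP 2.1 sets one rule for all 2 x 2 comparisons with Vehicle. Pearson's test is used under the condition "If there are at least 5 observations in each cell in the 2 x 2 table", and Fisher's under the condition "If there are not at least 5 observations in each cell in the 2 x 2 table". As worded, these are observed counts. Neither document mentions expected counts.

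Protocol 11.4 is looser: "In case of small sample sizes alternatively Fisher's exact test may be applied". It gives no cell criterion and leaves the choice open. The SAP makes the choice mandatory and adds the threshold.

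On sidedness, SAP 2.6 says "For statistical assessment of the primary endpoint with a significance level of 0.05 the following underlying hypotheses are used" and then states a directional alternative (active better than Vehicle). SAP 2.8 gives alpha as 0.05 without saying whether it is one- or two-sided.

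**The concern.** The chi-square approximation behind Pearson's test depends on the expected counts, which come from the table margins. One small observed cell does not make it unreliable. A rule based on observed counts therefore sends some tables to Fisher although Pearson is adequate for them. Fisher is conservative at these sample sizes, so power is lost without any gain in protection that is needed.

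The rule also creates a discontinuity. With 60 per arm, 13 vs 5 clearances is tested by Pearson (two-sided p = 0.041). The same 8-subject difference at 12 vs 4 is sent to Fisher (p = 0.058), although its ratio is larger.

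At stake are the comparisons in which few Vehicle subjects clear. These may include the early-visit clearance endpoints and, if tests are run there, the subgroup tables.

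**Working it through.** **Inputs.** SAP 2.8 assumes that active "exhibits a complete clearance of the AK lesions in 45% of the subjects, while the Vehicle does so in 20% of the subjects". It continues "Assuming a power of 80% and α of 0.05", and concludes that "54 patients per treatment group would be needed" and, "assuming a drop-out rate of 10%, 60 subjects need to be recruited in each treatment group". Low-rate pairs come from the diclofenac results in Table 1 of the protocol Introduction: 7/49 vs 2/49 (14%/4%, 30 days of treatment) and 15/48 vs 5/49 (31%/10%, 60 days). The pair 20%/5% is my assumption.

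**Reproducing the plan's figure.** With pooled variance, two-sided 0.05 and no continuity correction:

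n = [1.960 × √(2 × 0.325 × 0.675) + 0.842 × √(0.45 × 0.55 + 0.20 × 0.80)]² / 0.25² = (1.298 + 0.537)² / 0.0625 = 53.9, so 54; and 54 / 0.90 = 60.

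The one-sided version gives 43. The sample size is thus two-sided, while the hypotheses are directional. Both readings are shown below.

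**When the two criteria disagree.** With equal arms, the expected number cleared in each arm is half the total cleared. At 60 per arm all four expected counts reach 5 once total clearances lie between 10 and 110. Any Vehicle count of 0 to 4 still forces Fisher. Below 10 total clearances, both criteria give Fisher.

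**Worked table, 12/60 vs 4/60.** Expected cleared per arm = 16/2 = 8; expected not cleared = 52. Pooled rate = 16/120 = 0.133; z = 0.133 / √(2 × 0.133 × 0.867 / 60) = 2.15.

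| Cleared, active vs Vehicle (60 per arm) | Smallest expected count | Two-sided Pearson / Fisher | One-sided Pearson / Fisher |
|---|---|---|---|
| 12 vs 4 | 8.0 | 0.032 / 0.058 | 0.016 / 0.029 |
| 10 vs 3 | 6.5 | 0.040 / 0.075 | 0.020 / 0.037 |
| 9 vs 3 | 6.0 | – | 0.034 / 0.063 |
| 10 vs 4 | 7.0 | – | 0.044 / 0.077 |

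The first two change verdict only two-sided, the last two only one-sided.

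**Power.** I enumerated all 61 × 61 outcomes at 60 per arm, weighted by their binomial probabilities. Each cell shows the SAP rule, then the expected-count rule. A needless switch means that Fisher is forced although all expected counts are at least 5.

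| Active / Vehicle | Needless switch | Two-sided power | One-sided power |
|---|---|---|---|
| 45% / 20% (planned) | 0.4% | 84.8% / 84.8% | 91.0% / 91.0% |
| 47% / 19% (Table 1, 90 days) | 0.7% | 91.8% / 91.8% | 95.6% / 95.6% |
| 34% / 18% (Table 1, 90 days) | 1.1% | 52.9% / 52.9% | 65.1% / 65.1% |
| 31% / 10% (Table 1, 60 days) | 27% | 83.1% / 83.5% | 90% / 90% |
| 14% / 4% (Table 1, 30 days) | 56% | 35.3% / 46.1% | 51.3% / 55.7% |
| 20% / 5% (assumed) | 77% | 64.4% / 72.4% | 77.9% / 81.8% |

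**Type I error, two-sided, 60 per arm.** At a common rate of 10% the size is 2.3% under the SAP rule and 4.6% under the expected-count rule. At 8% it is 1.9% and 3.8%, and at 20% it is 4.9% and 5.0%.

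**The case against.** The strongest reply is that this hardly matters for the trial's main question. Treatment lasts 12 weeks, and the 90-day studies in Table 1 had Vehicle rates of 18% and 19%. At those pairs and at the planning rates, power is the same under both criteria. That stands, and three stronger readings fail with it.

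- A reader might infer that the primary analysis is weakened. The plan's own assumptions do not support that.
- A reader might infer that a clear effect could be reported as non-significant. The tables that change verdict are borderline. A table of 27 vs 4 gives p < 0.00001 by either test. If the planned 25-point difference is kept with low Vehicle rates, two-sided power barely moves: 94.2% vs 94.4% at 33%/8%, and 97.0% vs 97.9% at 29%/4%.
- A reader might infer that the switch penalises only favourable results. It fires when any of the four cells is below 5, including low clearance on active or in both arms.

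The size also depends on sidedness. Under the directional hypotheses of SAP 2.6, 12 vs 4 and 10 vs 3 are significant by either test, and the gap at 20%/5% falls from 8 points to 4. Other tables change verdict one-sided, so the problem shrinks but remains.

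Finally, the rule is pre-specified, leaves no discretion and errs on the safe side, in a trial that SAP 2.8 calls exploratory. This limits the severity. It does not justify the criterion, because the expected-count version keeps type I error at or very near 5%.

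**Conclusion.** The point holds as a technical error in SAP 2.1 with limited reach. The rule tests the wrong quantity and sends some tables to Fisher without need. At the planned 45% vs 20% the primary comparison is unaffected.

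The cost falls on comparisons with Vehicle clearance of about 5% or less and a modest active effect. In the two such scenarios in the table it is about 8 to 11 points of power two-sided and about 4 one-sided. Near 10% Vehicle clearance with a 31% active rate it is under half a point.

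These figures assume 60 per arm. The 14%/4% and 31%/10% pairs come from another drug, assessed 30 days after treatment, and stand in here for low-rate situations; 20%/5% is assumed. Subgroups are smaller. Some of their tables will also fail the expected-count criterion and go to Fisher under either rule, so I put no figure on them.

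**What to change.** In SAP 2.1, apply the threshold of 5 to expected counts: Pearson when all four expected counts are at least 5, Fisher otherwise. Alternatively, name one test in advance for all 2 x 2 comparisons. State in the same place whether the p-values are one- or two-sided, since SAP 2.6 and SAP 2.8 point in different directions.

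The cost is one sentence before database lock, with no new data. The downside is that type I error moves closer to nominal. Over common rates of 4% to 20%, two-sided size is at most 5.0% at 60 per arm; at 54 per arm it is 5.07% at a 20% rate. One-sided, it reaches 5.03% and 5.24% respectively. In that last case the present rule already gives 5.12%.

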2.2. Study Populations

Safety Population

All subjects who receive at least one confirmed dose of study product and provide any post-baseline safety information will be included in the safety population. No imputation will be made for missing safety data.

Intention- to -Treat Population (ITT)

The intention-to-treat population (ITT) will be the primary efficacy analysis data set and consists of all subjects who are randomized and dispensed study medication.

If the method to handle missing observations is not explicitly defined (i.e. Percent Change from Baseline in Actinic Keratosis Lesion Count), two principles will be applied to adjust for missing observations: last observation carried forward (LOCF) and multiple imputations (MI). Last observation carried forward will be derived in the analysis datasets while the multiple imputations method will be performed using SAS procedures PROC MI and PROC MIANALYZE.

Per-Protocol Population (PP)

The per protocol (PP) population will include all subjects in the ITT population who complete the Week 16 evaluation without any major protocol violations (i.e., any subject or Investigator activity that could have possibly interfered with the therapeutic administration of the treatment or the precise evaluation of treatment efficacy).

Specifically, the PP population will include subjects in the ITT population who meet all of the following criteria:

1. Subject met all inclusion/exclusion criteria.
2. Subject did not take any prohibited concomitant medications during the evaluation period. The concomitant medication usage will be reviewed during the population determination review, remaining blinded to treatment designation, to determine prohibited medication usage that warrants exclusion from the PP population, if they met the entry criteria without any protocol violations. This review will take into consideration the timing, the dose, and duration of treatment with the concomitant medication, and its possible influence on the efficacy and safety assessments (from the known pharmacokinetic and pharmacodynamics interactions of the concomitant medication) prior to deeming a prohibited medication as a protocol violation that warrants exclusion from PP.
3. Completed the Week 16 visit within the allowed window (of ± 5 days).
4. Subject was compliant with the dosing regimen. A subject will be considered compliant if the subject applied at least 80%, but no more than 120% of the expected number of applications during the entire treatment period.

Subjects who prematurely discontinue from the study due to documented lack of efficacy, worsening condition, or a treatment-related AE will be included in the PP population. These subjects will be considered failures for all subsequent visits in the analysis of the primary and secondary endpoints of complete and partial clearance of AK lesions. Other than this, no imputations for missing data will be made for the PP populations.

Other additional criteria may be added to the list to accommodate for unforeseen events that occurred during the conduct of the trial that result in noteworthy study protocol violations. These criteria will be documented in the Documentation of Statistical Decisions.

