## 7.6 Early Withdrawal of Subjects

1. Subjects should be withdrawn from the study if they no longer wish to participate, are being uncooperative, or if the Investigator feels that it is in the best interest of the subject to withdraw.
2. Subjects with protocol deviations or for whom it is discovered should have been excluded should not be withdrawn unless there is a safety concern. The protocol deviation should be recorded in the subject's source documents and the eCRF.
3. If during the course of treatment a subject experiences a cardiovascular or hematologic AE (including abnormal laboratory values) of Common Terminology Criteria for Adverse Events (CTCAE) Version 4.02 Grade 2 or higher, the study product will be discontinued and the subject will be withdrawn from the study.
4. Subjects who experience an AE resulting in or requiring discontinuation of study product use should be encouraged to be followed until the AE is resolved or stabilized.
5. If a female subject becomes pregnant during the study, study product will be discontinued immediately and she will be followed through the pregnancy and delivery. Details of the pregnancy, delivery and health of the infant should be recorded on the Pregnancy Surveillance Form. The Sponsor will be notified immediately after the subject is detected to be pregnant.
6. At the time of study discontinuation, the Investigator will record the reason for early withdrawal, date of last study product application, date of last visit or contact, collect adverse event data, and, if possible, perform all End of Study Visit specific evaluations. Every attempt should be made to contact subjects who are lost-to-follow-up. At least three attempts must be documented in the subject's source document, including the use of at least one certified letter. Any contact, either direct or indirect, should be made with the purpose to document the final status of the subject with regard to safety. Subjects who withdraw early will not be replaced.

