#### **7.10.6 Visit 6 – Week 16/End of Study Visit (Allowed visit window is $\pm$ 5 days)**

1. Evaluate protocol compliance and record any deviations.
2. Investigator is to document the size and location of the lesions with in the treatment area and on a grid foil. One copy of the grid foil should be inserted into the subject's source document.
3. Collect vital signs (blood pressure and pulse rate).
4. Conduct a urine pregnancy test for all females of child bearing potential.
5. Collect AE data. This includes a review of the diary card for potential AEs.
6. Complete eCRF.

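### The plan has no scoring rule for a lesion count taken after a prohibited AK therapy on the treatment area, so in ITT another drug's clearance can count as a primary-endpoint success

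*SAP*

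**What the plan says.** - **Prohibition.** Protocol 6.7 bars 5-fluorouracil, imiquimod, ingenol mebutate, photodynamic therapy, diclofenac and others from 60 days before Baseline until Visit 6.
- **Breaches do not end participation.** Protocol 7.6, item 2: "Subjects with protocol deviations or for whom it is discovered should have been excluded should not be withdrawn unless there is a safety concern". Under Protocol 7.3 all visible or palpable lesions in the area are counted at every visit, with no exception for lesions treated by other means.
- **ITT.** SAP 2.2 says this population "will be the primary efficacy analysis data set and consists of all subjects who are randomized and dispensed study medication". Its data-handling rules are last observation carried forward (Protocol 11.2.1), and LOCF with multiple imputation where no method is otherwise defined (SAP 2.1 and 2.2). All of these concern missing values. SAP 2.6 adds no scoring rule.
- **Primary endpoint.** SAP 1.3.1 defines complete clearance as no visible or palpable AK lesion in the treatment area at Week 16. It does not ask what cleared them.
- **PP, prohibited medication.** Criterion 2 is "Subject did not take any prohibited concomitant medications during the evaluation period". A blinded review then weighs timing, dose, duration and possible influence on the assessments "prior to deeming a prohibited medication as a protocol violation that warrants exclusion from PP".
- **PP, withdrawal.** "Subjects who prematurely discontinue from the study due to documented lack of efficacy, worsening condition, or a treatment-related AE will be included in the PP". On scoring: "These subjects will be considered failures for all subsequent visits in the analysis of the primary and secondary endpoints of complete and partial clearance".
- **Visit 6.** The study schedule marks concomitant medications at Visit 6. The step list in Protocol 7.10.6 goes from "Collect AE data. This includes a review of the diary card for potential AEs" to completing the eCRF, with no medication update. The lists for Visits 3, 4 and 5 and for early withdrawal all include that update.

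**The concern.** One clinical event, lesions that fail to clear on study product, can be scored in three ways. A subject who stays and clears with another therapy is a possible success in ITT. The same subject may be absent from PP. A subject who leaves for lack of efficacy is a PP failure. What separates them is whether the subject withdrew, not how the study product performed.

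The primary analysis is the one most exposed. Turning to another AK therapy is a response to poor outcome, so it is unlikely to be unrelated to treatment arm. If it happens more on Vehicle, the Vehicle clearance rate is raised by drugs that are not under test. With 60 subjects per arm, a few such subjects move the estimate noticeably. PP is no clean check on this, because removing users changes each arm's rate by an amount that depends on how many users that arm had.

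**Working it through.** **Inputs.** From SAP 2.8: Active 45%, Vehicle 20%, alpha 0.05, power 80%, 54 per group, 10% dropout, 60 recruited per group. The documents give no rate of prohibited AK therapy use and no clearance rate after it, so all user counts below are assumptions.

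**The plan's own figure.** With mean proportion 0.325 and two-sided alpha 0.05:

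n = [1.960·√(2·0.325·0.675) + 0.842·√(0.45·0.55 + 0.20·0.80)]² / 0.25² = 53.9, rounded up to 54. Then 54/0.90 = 60.

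The figure reproduces as a two-sided calculation; a one-sided one gives 43. Power below is two-sided, by the matching formula:

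power = Φ{[d·√n − 1.960·√(2·p̄(1−p̄))] / √(p₁(1−p₁) + p₂(1−p₂))}, where d = p₁ − p₂ and p̄ is the mean of p₁ and p₂.

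This gives 80.1% at 54 per arm and 84.1% at 60.

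**Reference at 60 per arm.** Active 27/60 = 45%, Vehicle 12/60 = 20%, difference 25.0 points. This is also the result if every user is scored as not cleared.

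**ITT with the observed count.** Suppose rV Vehicle failures and rA Active failures use a prohibited AK therapy and all of them clear. The rates become (12 + rV)/60 and (27 + rA)/60.

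| rV | rA | Vehicle | Active | Difference | Power |
|---|---|---|---|---|---|
| 0 | 0 | 20.0% | 45.0% | 25.0 | 84.1% |
| 1 | 0 | 21.7% | 45.0% | 23.3 | 78% |
| 3 | 0 | 25.0% | 45.0% | 20.0 | 63.5% |
| 5 | 0 | 28.3% | 45.0% | 16.7 | 47.3% |
| 5 | 2 | 28.3% | 48.3% | 20.0 | 61.8% |

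With equal clearance after use, ITT is attenuated whenever more Vehicle than Active subjects are users. With equal numbers of users the difference does not move.

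**PP if the review excludes every user.** The users are failures, so the rates become 12/(60 − rV) and 27/(60 − rA).

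| rV | rA | Vehicle | Active | Difference |
|---|---|---|---|---|
| 3 | 0 | 12/57 = 21.1% | 27/60 = 45.0% | 23.9 |
| 5 | 2 | 12/55 = 21.8% | 27/58 = 46.6% | 24.7 |
| 3 | 2 | 12/57 = 21.1% | 27/58 = 46.6% | 25.5 |
| 3 | 3 | 12/57 = 21.1% | 27/57 = 47.4% | 26.3 |

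The shift changes sign. Let sV and sA be the shares of each arm that are excluded users. The PP difference equals 25 points when 0.45/(1 − sA) − 0.20/(1 − sV) = 0.25, that is, when sA = 1 − 0.45/[0.25 + 0.20/(1 − sV)]. For sV = 5%, 10% and 20% the break-even sA is 2.3%, 4.7% and 10.0%. PP therefore favours Vehicle only if Vehicle use is about 2.0 to 2.2 times Active use or more. Below that it favours Active.

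**The case against.** **Using the observed count is a conventional ITT choice.** Analysing every randomized subject on the outcome seen, whatever else was taken, is a treatment-policy approach; scoring users as failures is a composite approach. Neither is an error in itself. This stands, but the plan does not say which it intends. The observed count applies only because nothing else is written, and the sponsor's own PP rule scores the comparable withdrawals as failures.

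**PP exclusion is not automatic.** A reader might infer from criterion 2 that every user is dropped. The text does not support that, because a blinded case review decides. Since the review weighs influence on the efficacy assessment, an AK therapy on the treated area is nonetheless a strong candidate for exclusion.

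**A route exists before lock.** SAP 2.1 requires a signed Documentation of Statistical Decisions before database lock, and unblinding follows lock. This lowers the risk. But that document records decisions prompted by the data collected, and a foreseeable scoring rule for the primary endpoint should be written in advance.

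**The illustration is severe.** Every assumed user clears, and most of the ITT rows have no Active users. The only AK-therapy clearance rates in the documents are 14% to 47% for diclofenac gel (Protocol Table 1). At those rates, three clearances need 3/0.47 to 3/0.14, about 6 to 21 Vehicle users, or 10% to 35% of the arm. Other therapies may clear more, but no figure is given. This stands: the power figures show sensitivity and are not forecasts.

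**Visit 6.** A reader might infer that sites do not ask about the four weeks before the primary count. That goes too far. The first step in 7.10.6 is a protocol-compliance check, the diary is reviewed (for adverse events), and the schedule does mark concomitant medications. It is a mismatch to reconcile, not proof of a data gap.

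**Conclusion.** The gap is real. As written, a count of zero reached with another AK therapy meets the primary endpoint in ITT, and the plan treats the same failure differently according to whether the subject withdrew. The ITT effect is attenuation if use is commoner on Vehicle: 23.3 points and 78% power with one Vehicle user who clears, 20.0 points and about 64% with three, against 25.0 points and 84%. The usage pattern is assumed; it is plausible but not documented.

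It is tempting to conclude that the ITT and PP rules both favour Vehicle. The documents do not support that. They give no usage rates by arm, PP exclusion depends on review, and the PP shift favours Vehicle only when Vehicle use is roughly twice Active use or more. PP bias of unknown sign is a reason for an explicit rule, not evidence of a direction. The sample size calculation is unaffected. For an exploratory Phase 2b trial this is a clarification that should be made before database lock.

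**What to change.** 1. In SAP 2.2 and 2.6, and in Protocol 11.2, state that a subject who receives a prohibited AK-active therapy on the treatment area after Baseline is scored as not completely and not partially cleared at every later visit in the primary ITT analysis. This extends the rule already applied to lack-of-efficacy withdrawals in PP.
2. Report the analysis on observed counts as a sensitivity analysis.
3. In PP, apply the same scoring to such subjects whom the blinded review keeps.
4. Reconcile the Visit 6 step list in Protocol 7.10.6 with the study schedule on the concomitant-medication update, so that use in the last four weeks is captured consistently.

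The cost is a few sentences before database lock and one reconciled step list, with no added subjects or assessments. The downside is that some subjects who look clear become failures, so clearance rates may fall slightly in every arm.
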